# 9.5.1. Feasibility counts

The expected distribution of patients across indications (RA, PsA, UC) for the databases in Hungary, Sweden, the Netherlands, and Germany is described below. Where limited information is available, the methods used to predict uptake of tofacitinib are discussed.

High-level feasibility counts for NHIFA of Hungary are available and provided in Table 6. As of June 2021, only the RA indication has received full reimbursement in Hungary, with the PsA and UC indications available via the Named Patient Program. Thus, there may be smaller patient numbers for these two indications relative to the RA indication in Hungary.

Condition (ICD-10 code)	Date approved by the EC	Date of full reimbursement	Number of patients
RA (M05)	Mar 2017 (5-mg) Dec 2019 (11-mg PR)	May 2019	156
PsA (L40)	Jun 2018 (5-mg)	Anticipated Q1 2023 a	10
UC (K51)	Jul 2018 (5-, 10-mg)	Anticipated Q1 2023 a	46
Total			218

Table 6.	Tofacitinib	patient cou	unts through	n March	2020 in	NHIFA o	of Hungary
I HOIC OF	I ofuciting	patient cou	unto the ough	I IVIAI CII		I VALAR IA C	I Hungury

Abbreviations: EC = European Commission; ICD-10: International Classification of Diseases, Tenth Revision; mg = milligram; NHIFA = National Health Insurance Fund Administration (of Hungary); PR = prolonged-release; PsA = psoriatic arthritis; Q = quarter; RA = rheumatoid arthritis; UC = ulcerative colitis.

a. As of June 2021, only available via the Named Patient Program.

Based on publicly available tools for querying the Swedish national health registries, the annual number of tofacitinib patients are reported in Table 7 (overall, but not stratified by indication).

# Table 7.Annual tofacitinib patient counts in the Swedish Prescription Drug
Register (2017-2019)

	2017	2018	2019
Number of tofacitinib patients a	336	889	1912

In Sweden, tofacitinib received full reimbursement for RA in April 2017 and full reimbursement for PsA and UC in October 2018.

Abbreviations: PsA = psoriatic arthritis; RA = rheumatoid arthritis; UC = ulcerative colitis.

a. Counts were obtained using the publicly available tools for querying the Swedish national health registers (available at https://sdb.socialstyrelsen.se/if\_lak/val.aspx). Note that only data on the annual number of tofacitinib patients (overall) are available.

Counts for the number of patients with RA, PsA, and UC in Sweden with moderate-to-severe disease (defined as treated with a biologic) are reported in Table 8, as this patient population represents those patients who are most likely to be eligible to receive tofacitinib and thus potentially be prescribed tofacitinib during the study observation period. The time periods for the studies listed in the table below varied by indication and ranged from 2006 (PsA) to 2019 (UC).

# Table 8.Summary of expected distribution of biologics across indications (RA,
PsA, UC) in Sweden

Country	Indication	Ν	Details
Sweden	$RA^{16}$	13274	2010-2016

 Available at https://sdb.socialstyrelsen.se/if\_lak/val.aspx.

# Table 8.Summary of expected distribution of biologics across indications (RA,
PsA, UC) in Sweden

Country	Indication	Ν	Details
			Swedish Rheumatology Quality register (SRQ)
			linked with the Swedish national health registers
			(PDR, NPR, NCR)
			Incident and prevalent biologic users
	PsA 	898 (first line)	May 2010 to Dec 2012
		146 (second line)	PDR
			SC-TNFi
	PsA 	5357	2006 to 2017
			SRQ
			Incident and prevalent biologic users
	UC a	2005 (TNFi)	1 July 2019 and 31 Dec 2019
		<63 b (tofacitinib)	Swedish Quality Register for Inflammatory
			Bowel Disease
			TNFi; tofacitinib

Abbreviations: MAH = Marketing Authorisation Holder; N = number; NCR = (Swedish) National Cancer Registry; NPR = (Swedish) National Patient Register; PDR = (Swedish) National Prescription Register; PsA = psoriatic arthritis; RA = rheumatoid arthritis; SC = subcutaneous; SRQ = Swedish Rheumatology Quality register; TNFi = tumour necrosis factor inhibitor; UC = ulcerative colitis.

a. Data provided by the MAH.

b. An exact number cannot be reported due to the masking of small cell counts to comply with privacy regulations.

High-level feasibility counts for PHARMO Database Network of the Netherlands are available and provided in Table 9.

Table 9.	Tofacitinib patients counts (through 2019) in the PHARMO Database
	Network of the Netherlands

Condition	Date approved Date of full		Number of patients a
	by the EC	reimbursement	
RΔ	Mar 2017 (5-mg)	May 2017	180
KA	Dec 2019 (11-mg PR)		180
PsA	Jun 2018 (5-mg)	August 2018	40
UC	Jul 2018 (5-, 10-mg)	September 2018	65
Total			280

Abbreviations: EC = European Commission; mg = milligram; PR = prolonged-release; PsA = psoriatic arthritis; RA = rheumatoid arthritis; UC = ulcerative colitis.

a. This number will decrease when the GP database and the Clinical Laboratory Database are required, as only 30% and 40% of patients observed in the High Budget Impact Medication Dataset are also observed in the GP database (covering approximately 20% of the Dutch population) and the Clinical Laboratory Database (covering approximately 5% of the Dutch population), respectively. Notably, the patient numbers outlined are from 2019, and these are expected to increase with tofacitinib uptake at the initial study execution in September 2022.

High-level feasibility counts for GKV claims of Germany are available and provided in Table 10.

Condition (ICD-10 code)	Date approved by the EC	Date of full reimbursement	Number of patients
RA (M05)	Mar 2017 (5-mg) Dec 2019 (11-mg PR)	May 2017	843
PsA (L40)	Jun 2018 (5-mg)	June 2018	169
UC (K51)	Jul 2018 (5-, 10-mg)	July 2018	190
Total			1111

 Table 10.
 Tofacitinib patients counts (2017-2019) in GKV Claims of Germany

Abbreviations: EC = European Commission; ICD-10: International Classification of Diseases, Tenth Revision; mg = milligram; GKV = Gesetzliche Krankenversicherung; PR = prolonged-release; PsA = psoriatic arthritis; RA = rheumatoid arthritis; UC = ulcerative colitis.

Market uptake of tofacitinib for the three indications in the proposed study countries (Hungary, Sweden, the Netherlands, and Germany) cannot be determined *a priori*. Additionally, as this is a multi-year study, changes in the treatment landscape (e.g., approval of new medications for RA, PsA, and UC treatment) may limit the number of patients prescribed tofacitinib. As such, it may be difficult to achieve the minimum target sample size of 100 patients per indication for certain indication-country combinations during the proposed study observation period, depending on overall tofacitinib uptake and when a particular indication, which received or will receive full reimbursement after RA (sometimes much later). Thus, if the *minimum* of 100 tofacitinib patients have not been accrued for a specific indication-country combination (e.g., UC in Sweden), then the CV and Malignancy Reporting Period 3 will be extended for that country as the data are available.

#### 9.6. Data management

The processes for database management differ by country. Generally, the data are stored at the database level and analysed locally. SAS® software (SAS Institute Inc., Cary, North Carolina, United States) or other appropriate analytical software will be used to access the raw data, manage the analytic datasets, and conduct data analyses. If the study is conducted by a third-party, the datasets and analytic programs will be stored according to the third-party's procedures. This study will follow the relevant chapters of the European Network of Centres for Pharmacoepidemiology and Pharmacovigilance (ENCePP) and the International Conference on Harmonisation (ICH) guidelines for data management. In addition, the data will be checked for consistency in terms of range of values, units of measurement, and relevance of clinical information (e.g., pregnancy diagnosis for a male patient).

### 9.7. Data analysis

Detailed methodology for summary and statistical analyses of data collected in this study will be documented in a SAP, which will be dated, filed, and maintained by the sponsor. The SAP may modify the plans outlined in the protocol; any major modifications of primary endpoint definitions or their analyses would be reflected in a protocol amendment. Interim study report 1 will cover data from 01 April 2016 through 31 December 2020. Interim study report 2 will cover data from 01 April 2016 through 31 December 2022. The final study report will cover data from 01 April 2016 through 31 December 2024. If it is necessary to extend the study observation period for a country because the *minimum* number of tofacitinib patients (100 patients) per indication has not been met for all three indications by the end of the study observation period, the study observation period will be extended for those countries as the data are available.

#### 9.7.1. Primary analysis

The primary analyses will be conducted per approved indication per country, unless otherwise specified. Data will *not* be pooled across countries due to heterogeneity in: how the data are recorded in each database, local data protection laws, and prescribing and coding practices.

Results will be provided as descriptive statistics; no comparative statistical analyses will be conducted. Categorical variables will be reported using frequency distributions. Ordinal variables will be reported using frequency distributions, means, standard deviations (SDs), minimums, 25th percentiles, medians, 75th percentiles, and maximums, unless otherwise specified. Continuous variables will be reported using means, SDs, minimums, 25th percentiles, medians, 75th percentiles, and maximums, unless otherwise specified. When relevant, 95% CIs will be calculated for the study outcomes outlined in Section 9.3.1 (Outcomes) and Table 3.

Missing values will be reported as missing and no imputation will be undertaken. Results will be summarized in tables and figures in Microsoft® Excel and/or Word format.

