As a result of the Article 20 benefit-risk reassessment, the MAH will additionally evaluate HCPs' compliance with the new PRAC recommendations and limitations for use to minimise the risk of VTE across all approved indications (i.e., tofacitinib should be used with caution in patients with known VTE risk factors regardless of indication and dosage), with additional focus on the use of tofacitinib 10 mg BID as a maintenance treatment for patients with UC, and use and prior treatments among patients aged 65 years and older treated with tofacitinib. The MAH will also examine tofacitinib prescribing patterns over time, as well as changes in the utilisation of tofacitinib among patients with VTE risk factors and among elderly patients aged  $\geq 65$  years following the updated recommendations and limitations for use. As a result of the 2021 signal evaluation procedure, the MAH will also assess HCPs' compliance with the new EMA recommendations and limitations for use related to tofacitinib use in patients with CV risk factors and use in patients with malignancy risk factors.b The MAH will also examine tofacitinib prescribing patterns over time in the 2021 signal evaluation procedure.

This protocol describes the drug utilisation study (i.e., component 2 described above). Data from this study, together with the findings from the tofacitinib prescriber survey (A3921334), will be used to assess whether the aRMM materials are effective. This non-interventional (NI) study is designated as a Post-Authorisation Safety Study (PASS) and is conducted by the MAH as a Category 3 commitment to the EMA.

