### 8. RESEARCH QUESTION AND OBJECTIVES

The research question is: Is there evidence that prescribers in the EU are compliant with the recommendations and limitations for use described in the tofacitinib aRMM materials?

The primary objectives are to:

- 1. Describe the characteristics of patients treated with tofacitinib, stratified by study country (i.e., Sweden, Hungary, the Netherlands, and Germany) and indication (i.e., RA, PsA, and UC; off-label indications), in terms of:
  - Demographics (e.g., age, sex); and
  - Comorbidities and prior and current medication use.

<sup>b The 2021 signal evaluation procedure also required the evaluation of tofacitinib use in elderly patients aged  $\geq$ 65 years, however, this assessment had already been added to the protocol following the findings from the 2019 Article 20 referral.

- 2. Evaluate prescribers' adherence to the tofacitinib aRMMs, specifically:
  - Compliance to the recommended posology per indication (average daily dose [ADD]) and duration of use;
  - Compliance to patient screening and laboratory monitoring prior to and during tofacitinib treatment; and
  - Compliance to recommendations for limitations of use, including:
    - Use in patients with VTE risk factors;
    - Use in patients aged 65 years and older;
    - Use in patients with CV risk factors;
    - Use in patients with malignancy risk factors;
    - Contraindicated use; and
    - Use with concomitant medications not compatible with tofacitinib.

The secondary objectives are to:

- 1. Describe prescribing patterns over time; and
- 2. Describe changes in the utilisation of tofacitinib following the updated recommendations and limitations for use implemented after the 2019 Article 20 referral and the 2021 signal evaluation procedure, specifically:
  - Use in patients with VTE risk factors;
  - Use in the elderly (patients aged 65 years and older);
  - Use in patients with CV risk factors; and
  - Use in patients with malignancy risk factors.

**Note:** In Gesetzliche Krankenversicherung (GKV) claims (Germany), outpatient diagnoses are reported quarterly, which could result in the misclassification of baseline clinical characteristics and select outcomes of interest, impacting all objectives except for primary objective 2.

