#### 9.5. Study size

The sample size was based on achieving a desired precision of the estimation for the binary endpoints. The following formula, based on the normal approximation to the binomial proportion, was used to calculate the minimum sample size for significance level  $\alpha$  for each indication per country:

$$n = \frac{P \cdot (1-P) \cdot \left(Z_{1-\alpha/2}\right)^2}{e^2},$$

where *P* is the expected proportion of patients with the outcome of interest; *e* is the margin of error, or half the desired width of the confidence interval (CI); and  $Z_{1-\alpha/2}$  is the standard normal *Z*-score corresponding to a cumulative probability of  $1-\alpha/2$ .

The outcomes of interest are described in Section 9.3.1 (Outcomes) and Table 3. As the proportion of patients with each of the outcomes of interest (p) is not known in advance, it will be set to 50%, which yields the most conservative (i.e., the largest) sample size for a specified margin of error.

Therefore, to obtain 95% CIs with a desired total width of 20% for each outcome of interest (per indication per country), the study will require a sample size of *at least* 97 patients, which is rounded up to a *minimum* target sample size of at least 100 patients per indication per country. Note that the sample size will be smaller for some of the outcomes measured (e.g.,

use of tofacitinib while pregnant [women only] and all outcomes that require patients to have six months of tofacitinib therapy) and thus precision will vary by outcome.

$$n = \frac{0.50 \cdot 0.50 \cdot 1.96^2}{0.10^2} = 96.04$$

As such, the *minimum* target sample size per country (across all three indications) will be 300 patients and the *minimum* target sample size overall (across all countries and all three indications) will be 1200 patients.

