The study will aim to describe how implementation of the 2019 Article 20 referral aRMM materials (which incorporate guidelines for reducing the increased risk of VTE and mortality on tofacitinib) and the 2021 signal evaluation procedure aRMM materials (which incorporate guidelines for reducing the increased risk of CV-related outcomes and malignancy-related outcomes on tofacitinib) is associated with use of tofacitinib within vulnerable populations. While many of the VTE, CV, and malignancy risk factors will be assessed, some risk factors, such as immobilisation and obesity are under-captured in administrative databases and thus will not be reported due to the concern of a high level of missingness. Additionally, there are operational challenges associated with trying to assess the effect of acquiring a VTE risk factor post-tofacitinib initiation (e.g., it will not be feasible to assess whether a patient discontinued a prescription that they already filled in response to developing a VTE risk factor or if they took the entire prescription); thus, changes in prescribing patterns in response to acquiring a VTE risk factor post-index (e.g., initiation of oral contraceptives or hormone replacement therapy) will be reported with limitations. In Sweden, prior VTE cannot be reliably distinguished from new VTE unless there is a  $\geq 12$ -month period between the two events (i.e., if a patient with a history of VTE experiences a new VTE after initiating treatment with tofacitinib, it will only be possible to distinguish which VTE occurred *prior to* the index date and which VTE occurred after the index date if the two VTE events are separated by  $\geq 12$  months) due to the nature of the Swedish health registers and their use of ICD-10 diagnosis codes. The CV and malignancy risk factor of current or past smoker are likely under captured, leading to low sensitivity and misclassification. In Sweden, for instance, tobacco use disorder would typically be addressed as part of primary care, and the NPR does not contain primary care information. Regarding anti-smoking prescriptions, it is likely that most patients purchase nicotine replacement products over the counter, which would not be captured in the PDR, resulting in misclassification. Similar to many of the screening and monitoring guidelines above, the ability to assess guidelines which rely on the

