discretion of the healthcare provider will be limited. For example, assessment of whether tofacitinib is being "used with caution in patients with known risk factors for VTE, regardless of indication and dosage" cannot be done directly in this study. This assessment will be approximated using the number and proportion of patients who had VTE risk factors ( $\geq 1$  and  $\geq 2$ ) and were prescribed tofacitinib before and after the 2019 Article 20 referral aRMM materials were implemented. However, this assessment is limited in the sense that if the proportion of patients with VTE risk factors prescribed tofacitinib does not decline over time, it does not necessarily mean that prescribers were not prescribing tofacitinib with caution among patients with VTE risk factors.

The results from this study may not be generalizable to other member states of the EU (e.g., prescribing patterns and implementation of the recommended screenings and monitorings may vary by country). Finally, only the RA indication has received full reimbursement in Hungary (in May 2019), with the PsA and UC indications available only via the Named Patient Program. Thus, Hungary will not have a VTE Reporting Period 1 for any indication and also will not have a VTE Reporting Period 2 for the PsA and UC indications, nor will Hungary have a CV and Malignancy Reporting Period 1 or a CV and Malignancy Reporting Period 2 for the PsA and UC indications, which limits the MAH's ability to examine changes in the utilisation of tofacitinib among patients with VTE risk factors, among elderly patients, and among patients with CV or malignancy risk factors in Hungary following the updated recommendations and limitations for use. Additionally, there may be smaller patient numbers for these two indications relative to the RA indication in Hungary. However, there will be more comprehensive data across indications from Sweden. In the Netherlands, the PHARMO Database Network requires linkage between different data sources. As the same patients may not be captured by all databases and the initial number of tofacitinib patients is not high, patient counts may be affected by linkage.

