10.5 Does the plan describe methods for analytic control of confounding?			$\boxtimes$	n/a
10.6 Does the plan describe methods for analytic control of outcome misclassification?			$\boxtimes$	n/a
10.7 Does the plan describe methods for handling missing data?	$\boxtimes$			9.7.1
10.8 Are relevant sensitivity analyses described?			$\square$	

Comments:

There are no measures of association in this study.

Section 11: Data management and quality control	Yes	No	N/ A	Section Number
11.1 Does the protocol provide information on data storage? (e.g. software and IT environment, database maintenance and anti-fraud protection, archiving)	$\boxtimes$			9.6
11.2 Are methods of quality assurance described?	$\square$			9.8
11.3 Is there a system in place for independent review of study results?	$\square$			n/a

Comments:

Section 12: Limitations	Yes	No	N/ A	Section Number
12.1 Does the protocol discuss the impact on the study results of:				
12.1.1 Selection bias?			$\square$	n/a
12.1.2 Information bias?	$\square$			9.9

Section 12: Limitations	Yes	No	N/ A	Section Number
12.1.3 Residual/unmeasured confounding? (e.g. anticipated direction and magnitude of such biases, validation sub-study, use of validation and external data, analytical methods).				n/a
12.2 Does the protocol discuss study feasibility? (e.g. study size, anticipated exposure uptake, duration of follow-up in a cohort study, patient recruitment, precision of the estimates)				9.5, 9.5.1

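### Secondary objective 2 is to describe changes between reporting periods, but the plan estimates no change and gives it no interval, and the 20% width in Section 9.5 does not carry over to outcomes split by period

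*Protocol*

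**What the plan says.** Protocol Section 8 sets secondary objective 2: "Describe changes in the utilisation of tofacitinib following the updated recommendations and limitations for use implemented after the 2019 Article 20 referral", and likewise after the 2021 signal evaluation. Section 7 says that the data, together with the prescriber survey, "will be used to assess whether the aRMM materials are effective". Section 9.9 says the study aims to describe how implementing the revised materials "is associated with use of tofacitinib within vulnerable populations". On the recommendation to use caution in patients with VTE risk factors, it adds: "This assessment will be approximated using the number and proportion of patients who had VTE risk factors", before and after the 2019 referral materials.

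On method, Section 9.7.1 states "Results will be provided as descriptive statistics; no comparative statistical analyses will be conducted". It also provides: "When relevant, 95% CIs will be calculated for the study outcomes outlined in Section 9.3.1 (Outcomes) and Table 3". Sections 9.7.1.3.1 to 9.7.1.3.4 then list each proportion by Reporting Period, with no difference, ratio or trend. The comment on the analysis plan in Annex 2 reads "There are no measures of association in this study".

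On size, Section 9.5 aims "to obtain 95% CIs with a desired total width of 20% for each outcome of interest (per indication per country"), which gives 97 patients, rounded up to 100. It notes that some outcomes will have fewer patients, with pregnancy and six-month therapy as examples, and that precision will vary. Reporting periods are not mentioned. The trigger for extending the study is also 100 patients per indication and country, not per period.

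**The concern.** The objective concerns a change, and the result contributes to a judgement on whether the risk minimisation materials work. The reader will receive two or three proportions side by side and must form the contrast unaided. If per-period intervals are printed, the natural step is to look for overlap, which is not a valid interval for the difference. Section 9.9 warns that the absence of a decline does not prove a lack of caution. It gives no matching warning that an observed decline may be chance.

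Precision compounds this. Section 9.5 refers to the outcomes in Section 9.3.1, and that list includes the period-stratified secondary outcomes. A reader could therefore take the 20% width to cover the before/after results, where it does not hold at the planned minimum.

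**Working it through.** **The plan's own figure.** n = P(1−P)z²/e² with P = 0.50, z = 1.96, e = 0.10 gives 0.25 × 3.8416 / 0.01 = 96.04, so 97. This agrees with Section 9.5, and the six rows of Table 5 reproduce as well.

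**Check that needs no accrual assumption.** A 20% width at P = 0.5 needs 97 patients. Two periods need 2 × 97 = 194, and a cell at the floor has 100. In the best case nobody falls in Period 2 and the rest split 50/50. Each width is then 1.96/√50 = 27.7 points, and the half-width for the difference is 0.98 × √(1/50 + 1/50) = 19.6 points. A difference with a total width of 20 points would need 2 × 0.25 × 1.96²/0.1² = 192.08, so 193 patients in each period.

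**Illustrations with accrual assumed even over time.** The protocol gives no counts by period, so even accrual is an assumption. At P = 0.5:

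- period width = 2 × 1.96 × √(0.25/n) = 1.96/√n
- half-width of Period 3 minus Period 1 = 0.98 × √(1/n₁ + 1/n₃)

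Period lengths come from Sections 9.2.1 and 9.2.2: VTE 26/16/39 months; CV and malignancy 51/9–12/18–21 months, with midpoints 10.5 and 19.5 used here. For UC, Section 9.2.5 excludes patients indexed before the original materials for that indication were distributed. Table 2 dates this to September 2018 in Sweden and Germany. VTE Period 1 ends on 31 May 2019, so it lasts 9 months for UC and the split is 9/16/39 (64 months). Section 9.7.1.3.1 pools RA with PsA for VTE, so the floor for that stratum is 2 × 100 = 200.

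| Cell | Patients per period | Widths (points) | Half-width of difference |
|---|---|---|---|
| RA, CV/malignancy, 100 patients | 63 / 13 / 24 | 25 / 54 / 40 | 0.98 × √(1/62.96 + 1/24.07) = 23.5, about ±24 |
| RA and PsA pooled, VTE, 200 patients | 64 / 40 / 96 | 24 / 31 / 20 | 0.98 × √(1/64.2 + 1/96.3) = 15.8, about ±16 |
| UC, VTE, Sweden or Germany, 100 patients | 14 / 25 / 61 | 52 / 39 / 25 | 0.98 × √(1/14.06 + 1/60.94) = 29.0, about ±29 |

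The second row is optimistic, because it spreads PsA over all 81 months although PsA also starts in 2018. Across the full range of CV period lengths, Period 2 width runs from 51 to 59 points and Period 3 from 38 to 42.

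**Sensitivity.** At P = 0.2 every figure shrinks by √(0.16/0.25) = 0.8, so the RA row becomes about 20/44/32. If a cell held 843 patients in all (the German RA count for 2017–2019 in Table 10, used only as an example), the CV periods would hold about 531/109/203. Widths would be about 9/19/14 points and the difference would be known to about ±8.

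**The case against.** The study is declared descriptive, its objective says describe, and nowhere does it state that a fall counts as success. Per-period intervals are allowed, and the results are to be read with a prescriber survey. The 20% width is stated per indication per country, the caveat on precision is illustrative, 100 is a floor, and all eligible patients enter. All of this is correct. It removes three stronger readings that a reader might infer.

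- That the plan judges the measures by whether a proportion fell. The text sets no such rule.
- That the design is a coin toss because a fall appears about half the time with no true change. That is so for any two bare estimates: the exact probability is still about 0.49 with 500 patients in each period at P = 0.5. It is not a defect particular to this plan.
- That a promise of 20% per period is broken. None was made; this is a gap in the sizing statement.

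The Annex 2 comment is not an error either. It agrees with Section 9.7.1, and the only tension is the loose wording on association in Section 9.9.

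What the objection does not supply is an estimate of the change. A difference with an interval is itself descriptive and needs no hypothesis. Its omission is not a detail left to the SAP, because Section 9.7.1 excludes comparative analysis outright.

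**Conclusion.** The point holds as a mismatch between objective and analysis, together with an incomplete precision statement. The plan sets out to describe change and provides neither an estimate of it nor an interval. At the 100-patient floor and P = 0.5, no allocation of patients can give a 20% width in two periods, or a Period 3 minus Period 1 half-width below about ±20 points. Under even accrual the half-width is about ±24 points for a 100-patient RA cell (CV/malignancy), ±16 for the pooled RA/PsA stratum at 200 (VTE), and ±29 for UC in Sweden or Germany (VTE).

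These figures rest on even accrual, P = 0.5 and the normal approximation, which is rough at 13 or 14 patients. They describe cells at the minimum, not all cells: RA in Germany should do much better. Small cells remain exposed, such as PsA and UC in the Netherlands, with 40 and 65 patients through 2019 (Table 9). The documents do not support a claim that the study will reach a wrong conclusion, only that it leaves the uncertainty of the change unreported.

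**What to change.** - **Section 9.7.1.3:** for each period-stratified proportion, add the Period 3 minus Period 1 difference, and Period 2 minus Period 1, each with a 95% confidence interval (Newcombe, for example). Report it per country and indication stratum wherever both periods exist. Hungary has no VTE Period 1, so these VTE contrasts cannot be reported there.
- **Presentation:** treat these as descriptive estimates. Do not add a test, and do not make the words fall or rise depend on whether the interval excludes zero. That would be an unadjusted significance rule across many factors, countries and periods.
- **Section 9.7.1:** amend the sentence that rules out comparative analysis so that it allows these estimates. Annex 2 then needs only a consequential update.
- **Section 9.5:** state that the 20% width applies to outcomes not split by period, and give the expected width per period. Use indication-specific period lengths and the strata actually analysed. Section 9.3.1 lists the VTE outcomes by approved indication while Section 9.7.1.3.1 pools RA with PsA, so settle this first.

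The cost is extra columns computed from counts already tabulated, and a less favourable precision statement. No new data or patients are needed.
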